8. STATISTICAL CONSIDERATIONS AND ANALYSIS PLAN

8.1. ANALYSIS PLAN

The statistical analysis plan will be finalized prior to database lock, and it will include a more technical and detailed description of the statistical analyses and procedures for accounting for missing, unused, and spurious data described in this section.

8.2. ANALYSIS POPULATION

The following populations are defined for statistical purposes:

Population	Description
Enrolled	All patients who sign consent
Treated/Full Analysis Set	All patients who receive at least 1 dose of SQL70 biopolymer and 1 dose of SQP33 protodrug
Efficacy Evaluable	All patients who receive at least 1 dose of SQL70 biopolymer and 1 dose of SQP33 protodrug and undergo at least 1 post baseline tumor evaluation
Safety	All patients who received at least 1 dose of SQL70 biopolymer and/or SQP33 protodrug
PK	All patients in the Safety Population who have the necessary Day 1 and on-study measurements to provide interpretable results for the specific parameters of interest
Biomarker	All patients with available biomarker data

8.3. DETERMINATION OF SAMPLE SIZE

Phase 1 Dose Escalation: Sample size for the dose escalation portion of the study is not predefined; total enrollment will depend on the DLTs observed and number of escalation cohorts.

Phase 2a Expansion Groups:

Groups 1 (Extremity STS) and 3a (Head and Neck)

Sample sizes are guided by Simon 2-stage (optimal) designs based on historical objective responses per indication. Because of the different participant populations (sarcoma and H&N cancers), different criteria are applied to determine the number of participants for each stage and the strength of the efficacy signal that would recommend proceeding to the next stage. Details are described in subsequent sections and in [Table 9](#).

Table 9: Simon 2-Stage Design

Cohort	Power	Historical ORR/Target ORR	Stage 1 responders/ Stage 1 n	Stage 2 responders/ Stage 2 n	Consider Futility	Go to Stage 2	Consider Futility	Consider Efficacy	Expected Sample Size
H&N	85%	20%/45%	≤3/13	≥4/13		≤8/26		≥9/26	16.28
Extremity Sarcoma	70%	20%/35%	≤3/15	≥4/15		≤13/46		≥14/46	25.91

For sample size calculation and for simplicity of description, recommendations for stopping or progressing to the next stage are based on the number of objective responses observed. However, since best overall response (BOR) does not necessarily capture the full extent of clinical benefit and since response can be delayed or of short duration, Shasqi will also review other aspects of clinical benefit that may better predict PFS or OS benefit, such as DOR, before making a final determination.

Enrollment will be continued after reaching the indicated number of participants at Stage 1 while the initial efficacy evaluation is ongoing. This will allow additional participants to enroll to account for unexpected trial impact, such as response non-evaluable participants due to early dropout, design parameter change (e.g., historical response rate update), etc. Although the sample size calculations are based on efficacy considerations, safety will also be continuously assessed and will be considered in the decision to continue or terminate a study treatment population.

Under the optimal Simon 2-stage design criterion:

Group 1 - Extremity STS: A sample size of 46 is required to test a null hypothesis of $H_0: \pi \leq 0.2$ (20%) versus an alternative hypothesis of $H_1: \pi \geq 0.35$ (35%) ([Seddon 2017](#); [Tapp 2017](#); [Chawla 2015](#)) with a one-sided significance level of 0.0498 and 70.5% power, where π is the true proportion of successes. This design results in an expected sample size of 25.91 and a probability of early termination of 0.648. If the number of responses is less than or equal to 3 out of 15 participants in the first stage, then the trial will be stopped. If the trial proceeds to the second stage, 46 subjects in total will be studied. If 13 or less responses are observed, then the drug is rejected.

Group 3a - Head & Neck: A sample size of 26 is required to test a null hypothesis of $H_0: \pi \leq 0.2$ (20%) versus an alternative hypothesis of $H_1: \pi \geq 0.45$ (45%) ([Sandler 1984](#); [Harrington 2001](#)) with a one-sided significance level of 0.049 and 85.1% power, where π is the true proportion of successes. This design results in an expected sample size of 16.28 and a probability of early termination of 0.747. If the number of responses is less than or equal to 3 out of 13 participants in the first stage, then the trial will be stopped. If the trial proceeds to the second stage, 26 subjects in total will be studied. If 8 or less responses are observed, then the drug is rejected.

Continuous Reassessment Method (CRM) design

Group 2 (Unresectable STS)

Sample sizes for Group 2 participants are guided by the Continuous Reassessment Method (CRM) design ([Wheeler 2019](#)). The use of evaluating additional participants in the Expansion

Group 2 and the use of the CRM model provides an indication of whether to alter the RP2D regimen (3-day dosing per 21-day cycle vs. 5-day dosing per 21-day cycle) based on a comparison of toxicity and efficacy data collected from enrolled participants. The indicated population for the Group 2 participants is locally advanced or metastatic, unresectable, soft-tissue sarcoma of intermediate or high grade with evidence of disease progression and no prior anthracycline treatment, and thus the test statistics parameters for the CRM are based on historical toxicity and efficacy rates of said population (Table 10). The participants will receive SQP33 at the RP2D administered IV as a 3-day dosing regimen per 21-day cycle or as a 5-day dosing regimen per 21-day cycle. Participants may be replaced if they are enrolled into the study but do not receive (for reasons other than AEs/SAEs) the intended dose during Cycle 1. If Cycle 1 cannot be completed due to a COVID-19 infection, an additional patient may be enrolled in the cohort.

Table 10: Continuous Reassessment Method Design Considerations

Parameters	Continuous Reassessment Method (CRM)
Historical Rates of Toxicity ²	
 • Anemia: Grade ≥ 3- [8%] • Febrile neutropenia Grade ≥ 3- [~20%]
Acceptable threshold for toxicity	Grade ≥ 3 Related Myelosuppression TEAEs* 
 • Anemia: Grade ≥ 3- <15% • Febrile neutropenia Grade ≥ 3- <15%
Maximum Inefficacy proportion ²⁻⁴	0.20
Minimum Efficacy proportion ²⁻⁴	0.35
Types I and II errors set at	0.05
Total number of pts per arm	11
Power	none

*Myelosuppression TEAEs as per NCI-CTCAE v5.0- Anemia: Grade 3: Hgb <8.0 g/dL; <4.9 mmol/L; <80 g/L; transfusion indicated. Grade 4: Life-threatening consequences; urgent intervention indicated; Febrile Neutropenia: Grade 3-ANC <1000/mm³ with a single temperature of >38.3 degrees C (101 degrees F) or a sustained temperature of >=38 degrees C (100.4 degrees F) for more than one hour. Grade 4: Life-threatening consequences; urgent intervention indicated.

Test statistics parameters are based on historical toxicity and efficacy rates (Table 10). The acceptable threshold for toxicity is set at 15%, respectively. A toxicity rate at or above 15% for myelosuppression (Grade ≥ 3) related treatment emergent adverse events (TEAEs) (anemia and febrile neutropenia) would be considered unsafe for that cohort, and enrollment would stop. The maximum inefficacy and minimum efficacy rates are based on historical objective response rates (ORR), with <20% ORR being undesirable, and >35% ORR being desirable.

After approximately half (n=6 per arm) of participants in Group 2 have been enrolled and observed for at least 2 cycles or approximately 6-weeks and have had at least one post-baseline tumor assessment, an evaluation of all available data (safety, efficacy, and PK from both the Expansion and Dose Escalation) will be performed by the SRC, to determine whether to continue to enroll up to a total of 11 participants per arm or to stop enrollment of a cohort.

Groups 1 and 3a will treat up to approximately 28 participants in Stage 1 and Group 2 will treat up to a total of 22 participants. For all Expansion Groups: Patients may be replaced if they are enrolled into the study but do not receive (for reasons other than AEs/SAEs) the intended dose

during Cycle 1. If Cycle 1 cannot be completed due to a COVID-19 infection, an additional patient may be enrolled in the group.

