4. SAMPLE SIZE JUSTIFICATION

Groups 1 (Extremity STS) and 3a (Head and Neck)

Sample sizes are guided by Simon 2-stage (optimal) designs based on historical objective responses per indication. Because of the different participant populations (sarcoma and H&N cancers), different criteria are applied to determine the number of participants for each stage and the strength of the efficacy signal that would recommend proceeding to the next stage. Details are described in subsequent sections and in the following Simon 2-Stage Design table:

| | | | Stage 1 responders/ Stage 1 n | | Stage 2 responders/ Stage 2 n | | |
|----------------------------|-------|---------------------------------|----------------------------------|---------------------|----------------------------------|----------------------|-------------------------|
| Group | Power | Historical ORR/Target ORR | Consider Futility | Go to Stage 2 | Consider Futility | Consider Efficacy | Expected Sample Size |
| #1 Extremity Sarcoma | 70% | 20%/35% | ≤3/15 | ≥4/15 | ≤13/46 | ≥14/46 | 25.91 |
| #3 a H&N | 85% | 20%/45% | ≤3/13 | ≥4/13 | ≤8/26 | ≥9/26 | 16.28 |

For sample size calculation and for simplicity of description, recommendations for stopping or progressing to the next stage are based on the number of objective responses observed.

However, since best overall response (BOR) does not necessarily capture the full extent of clinical benefit and since response can be delayed or of short duration, Shasqi will also review other aspects of clinical benefit that may better predict PFS or OS benefit, such as DOR, before making a final determination.

Enrollment will be continued after reaching the indicated number of participants at Stage 1 while the initial efficacy evaluation is ongoing. This will allow additional participants to enroll to account for unexpected trial impact, such as response non-evaluable participants due to early dropout, design parameter change (e.g., historical response rate update), etc.

Although the sample size calculations are based on efficacy considerations, safety will also be continuously assessed and will be considered in the decision to continue or terminate a study treatment population.

Under the optimal Simon 2-stage design criterion:

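### Protocol 8.3 and Phase 2a SAP section 4 conflict on whether the stage-1 futility stop is binding, and the printed alphas for Groups 1 and 3a hold only if it is

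*Protocol*

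**What the plan says.** Protocol 8.3 sizes Groups 1 and 3a with Simon optimal two-stage designs. For Group 1 it tests a 20% against a 35% response rate, "with a one-sided significance level of 0.0498 and 70.5% power". For Group 3a it tests 20% against 45%, "with a one-sided significance level of 0.049 and 85.1% power".

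The design paragraphs word the decision rules as fixed:

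- Group 1, stage 1: if responses are "less than or equal to 3 out of 15 participants in the first stage, then the trial will be stopped".
- Group 1, final: "If 13 or less responses are observed, then the drug is rejected".
- Group 3a, stage 1: if responses are "less than or equal to 3 out of 13 participants in the first stage, then the trial will be stopped".
- Group 3a, final: "If 8 or less responses are observed, then the drug is rejected".

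Earlier in the same section the boundary is advisory. Table 9 labels the low counts as grounds to consider futility, and the text calls the counts the basis for recommendations. It adds that response may be delayed or short-lived, so the sponsor will look at other measures of benefit, "such as DOR, before making a final determination".

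Protocol 3.5.1 bases the Group 3a stage-1 recommendation on ORR together with all the other data. Phase 2a SAP section 4 carries both wordings, including the review "before making a final determination", and does not choose between them. Neither document uses the word binding or non-binding, sets criteria for an override, or gives an alpha for the case where the stop is not followed.

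**The concern.** In a Simon design, part of the type I error control comes from the stage-1 stop. Some null trials that start badly would recover and cross the final cut-off if they were allowed to continue, and the stop removes them. If the sponsor may continue after a failed stage 1 and then judge the group against the same final cut-off, those trials count as false positives again and the printed alpha no longer describes the rule in use.

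Two people holding 3 responses in 15 could act differently, each citing Protocol 8.3. The situation would be common for an inactive drug: by the plan's own figures the boundary is met with probability 0.648 in Group 1 and 0.747 in Group 3a when the true rate is 20%. The early-termination probability and expected sample size rest on the same assumption.

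**Working it through.** **Inputs (Protocol 8.3, repeated in Phase 2a SAP section 4).** Here p0 and p1 are the null and target response rates, r1/n1 is the stage-1 futility boundary, and r/n is the final rejection boundary.

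| | p0 | p1 | r1/n1 | r/n | Success |
|---|---|---|---|---|---|
| Group 1 | 0.20 | 0.35 | 3/15 | 13/46 | ≥14/46 |
| Group 3a | 0.20 | 0.45 | 3/13 | 8/26 | ≥9/26 |

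**Step 1: reproduce the plan's figures with the stop always followed.**

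- PET = P(Bin(n1, p0) ≤ r1)
- Expected N = n1 + (1 − PET)(n − n1)
- P(success) = Σ over x > r1 of P(Bin(n1, p) = x) × P(Bin(n − n1, p) ≥ r + 1 − x). This is alpha at p0 and power at p1.

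| | PET | Expected N | Alpha | Power |
|---|---|---|---|---|
| Group 1, computed | 0.6482 | 15 + 0.3518 × 31 = 25.91 | 0.0498 | 70.5% |
| Group 1, printed | 0.648 | 25.91 | 0.0498 | 70.5% |
| Group 3a, computed | 0.7473 | 13 + 0.2527 × 13 = 16.28 | 0.04976 | 85.1% |
| Group 3a, printed | 0.747 | 16.28 | 0.049 | 85.1% |

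Everything matches. The printed 0.049 for Group 3a is 0.04976 cut short; to four decimals it is 0.0498. The plan's figures are therefore those of a stop that is always followed.

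**Step 2: override the stop and keep the final cut-offs.** If every failed stage 1 continues, the design becomes a single-stage test on all n patients:

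- Group 1: P(Bin(46, 0.20) ≥ 14) = 0.0615, with power 78.7% at 0.35.
- Group 3a: P(Bin(26, 0.20) ≥ 9) = 0.0592, with power 89.8% at 0.45.

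Expected N is then simply 46 and 26.

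**Step 3: partial override.** Alpha if the group continues whenever stage 1 reaches the count shown:

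| Continue at | Group 1 | Group 3a |
|---|---|---|
| ≥4 (as printed) | 0.0498 | 0.0498 |
| ≥3 | 0.0580 | 0.0571 |
| ≥2 | 0.0609 | 0.0590 |
| ≥1 | 0.0615 | 0.0592 |
| any count | 0.0615 | 0.0592 |

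Most of the increase comes from exactly 3 responders: 0.0580 − 0.0498 = 0.0082 of the total 0.0117 in Group 1, and 0.0571 − 0.0498 = 0.0073 of 0.0094 in Group 3a. That is also the count at which discretion is most likely to be used.

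**Step 4: discretion in the other direction.** If the group is also stopped at exactly 4 responders, alpha falls to 0.0358 (Group 1) and 0.0345 (Group 3a).

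**Step 5: would a higher final cut-off help?** One more response is the smallest increase that keeps alpha at or below 0.05 without a stop.

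| | Alpha, never stopped | Power, never stopped | Power, stop applied |
|---|---|---|---|
| Group 1, ≥15/46 | 0.0304 | 68.5% | 62.6% |
| Group 3a, ≥10/26 | 0.0232 | 80.6% | 77.9% |

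All four power values are below the stated 70.5% and 85.1%.

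**The case against.** The strongest reply is that these alphas feed no planned analysis. The Phase 2a primary endpoints are safety measures, Protocol 8.4.2.1 plans no efficacy analysis for the primary endpoint, and ORR is a secondary endpoint reported as a rate with an exact 95% interval (Protocol 8.4.2.2; Phase 2a SAP 11 and 11.1). The sample sizes are described as guided by the Simon designs. This stands, and it limits the consequence to a stated planning figure. It does not remove the point, because Protocol 8.3 sets out hypotheses, an alpha to four decimals and a rule for rejecting the drug. Figures that exact should match the rule that will be applied.

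Second, the design paragraphs say plainly that the trial stops, and on that reading every printed figure is right. This also stands. A reader might infer that the stated alphas are wrong, or that the trial's true alpha is about 0.06. The documents do not support that: they contain one rule under which the figures are correct and another under which they are not guaranteed.

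Third, discretion need not raise alpha. The plan's mention of short-lived response would favour stopping despite 4 or more responses, and safety may also close a group; both lower alpha (step 4). The one measure the plan names, DOR, is evaluated only in responders, so it says little when there are 3 or fewer. This is fair, and it is why 0.0615 and 0.0592 must be read as upper limits and not as expected values.

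Finally, flexible futility is reasonable in a phase 2a trial looking for preliminary signals. Agreed; the request is only to say which rule applies and to quote the error rate that goes with it.

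**Conclusion.** The point holds as an inconsistency in both documents, with a small and bounded effect. The printed alphas, early-termination probabilities and expected sample sizes are correct for a binding stop and are not guaranteed by the advisory wording. Under override, alpha is at most 0.0615 in Group 1 and 0.0592 in Group 3a, against 0.0498 in each: an increase of about 1.2 and 0.9 percentage points. Overriding only at exactly 3 responders gives 0.058 and 0.057.

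These figures assume independent responses at a true rate of 20%, full enrolment to 46 or 26, and unchanged final cut-offs. If the sponsor's final determination were also taken to cover the end-of-study decision, alpha could move further, by an amount that cannot be calculated because no criteria are given.

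A reader might take this as a breach of a 5% guarantee for a confirmatory test. The documents state 0.0498 and 0.049 as design properties for a secondary endpoint and plan no such test.

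**What to change.** Reconcile the paragraphs in Protocol 8.3 and Phase 2a SAP section 4, and the Group 3a text in Protocol 3.5.1, in one of two ways, preferably before the stage-1 data are reviewed:

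1. **Binding.** State that 3 or fewer responses in 15 (Group 1) or in 13 (Group 3a) stops the group on ORR alone, and limit the review of other benefit data to groups that pass. The printed figures then stand, with the Group 3a alpha better given as 0.0498.
2. **Non-binding.** State that the boundary is advisory, restate the one-sided alpha as up to 0.062 (Group 1) and up to 0.059 (Group 3a), and note that the early-termination probability and expected N assume the stop is followed.

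Either option changes wording only. The first gives up flexibility; the second prints a slightly less favourable alpha. Raising the final cut-offs to 15/46 and 10/26 is not advised. It would hold alpha under 0.05 without a stop, but it over-corrects (0.030 and 0.023) and takes power below the stated values, to 62.6% and 77.9% when the stop is applied.

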 - Patients will enroll at the RP2D of SQ3370, maintaining the total dose per cycle constant and compare 2 different infusion schedules a 3-day vs a standard 5-day schedule. The 3-day cycle will administer the same dose on Day 1 as the 5-day cycle and 2x the doses on days 2 and 3 of the cycle. (See [APPENDIX I – Schedule of Assessments – Expansion Group 2: Unresectable STS \(5 day\)](#) and [APPENDIX J – Schedule of Assessments – Expansion Group 2: Unresectable STS \(3 Day\)](#) for details).
 - Eleven (11) patients per group. Subjects will be treated with the RP2D of SQ3370 every 21 days (1 cycle) up to 12 cycles or until other treatment discontinuation criteria are met (see section [3.1.5 End of Treatment](#)). On Day 1 of each cycle, the subject will receive an injection of SQL70 biopolymer into the tumor (10 mL) followed by 3 or 5 days of SQP33 infusion starting 3 hours ± 30 min after the SQL70 biopolymer injection.
- Group 3a: Head and Neck
 - Patients with histologically or cytologically confirmed relapsed or metastatic squamous-cell carcinoma of the head and neck (R/M HNSCC), who have exhausted curative intent therapies or patients with distant metastases who may have received one or less chemotherapy regimen.
 - This will follow a Simon 2-stage design. Thirteen (13) patients will be initially treated with the RP2D of SQ3370 every 21 days (1 cycle) up to 12 cycles or until other treatment discontinuation criteria are met (see section [3.1.5 End of Treatment](#)). On Day 1 of each cycle, the patient will receive a 10 mL injection of the SQL70 biopolymer into the tumor, followed by five (5) days of SQP33 infusion starting 3 hours ± 30 min after the SQL70 biopolymer injection. If ≥ 4 patients have a response (CR or PR), then 13 additional patients will be enrolled. (See [APPENDIX K – Schedule of Assessments – Expansion Group 3A: Head and Neck](#) for details).

Sample Size

Phase 1: Dose Escalation: Sample size for the dose-escalation portion of the study is not predefined. Total enrollment will depend on the DLTs observed and number of escalation cohorts.

Phase 2a: Expansion Groups 1 and 3a will be utilizing a Simon 2-stage (optimal) design to determine sample size (see below) based on historical objective responses per indication. Expansion Group 2 will utilize the Continuous Reassessment Method (CRM) design.

Simon 2-Stage Optimal Design

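### The expected sample sizes for Groups 1 and 3a (25.91 and 16.28) assume no enrolment while Stage 1 is evaluated, but the plan continues enrolment without a cap and leaves room to change the historical rate

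*Protocol*

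**What the plan says.** Protocol 8.3 gives Group 1 a stopping rule of 3 or fewer responses in 15 and a final rule of 13 or fewer in 46, "with a one-sided significance level of 0.0498 and 70.5% power". It adds: "This design results in an expected sample size of 25.91 and a probability of early termination of 0.648". Group 3a has 3 or fewer in 13 and 8 or fewer in 26, "with a one-sided significance level of 0.049 and 85.1% power", and: "This design results in an expected sample size of 16.28 and a probability of early termination of 0.747". Section 4 of the Phase 2a SAP repeats all of these figures.

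The same section of each document says: "Enrollment will be continued after reaching the indicated number of participants at Stage 1 while the initial efficacy evaluation is ongoing". Protocol 3.5.1 (Group 3a) and Phase 2a SAP 2.3 (Group 3a) say the same. The purpose given in Protocol 8.3 is to allow for events such as patients not evaluable for response and a "design parameter change (e.g., historical response rate update), etc".

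Other places read as if enrolment waited for the result. The Protocol Synopsis says of Group 3a: "If ≥ 4 patients have a response (CR or PR), then 13 additional patients will be enrolled". Protocol 8.3 and SAP 4 put Stage 1 of the two groups together at about 28 patients, which is 15 + 13 with nothing left for overrun.

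**The concern.** A Simon optimal design is chosen because it minimises expected sample size when the drug is no better than the historical rate. The printed expected N is therefore the plan's statement of how many patients it expects to expose to an inactive treatment. If enrolment runs on during the evaluation, the patients added are exposed even when Stage 1 fails, and the printed figure is too low.

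The evaluation is unlikely to be short. Objective response requires confirmation (Protocol 8.4.2.2) and scans are every 6 weeks (Protocol 6.18). A response first seen at the first scan would usually be confirmed at about week 12.

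The second issue is the reference to a historical rate update. The trial is open-label, so responses are visible to the sponsor while Stage 1 is being evaluated. The plan does not say when a rate could change, or what would happen to the cuts if it did.

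**Working it through.** **Inputs.** Protocol 8.3: Group 1 null 20%, target 35%, stop at ≤3/15, reject the drug at ≤13/46. Group 3a null 20%, target 45%, stop at ≤3/13, reject the drug at ≤8/26. The overrun m is an assumption, because neither document gives an accrual rate.

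**Step 1: reproduce the printed figures (exact binomial).** The probability of early termination is PET = P(X₁ ≤ r₁), and expected N = n₁ + (1 − PET)(n − n₁).

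- Group 1 at 20%: PET = 0.0352 + 0.1319 + 0.2309 + 0.2501 = 0.648. Expected N = 15 + 0.3518 × 31 = 25.91. Alpha 0.0498, power 70.5%.
- Group 3a at 20%: PET = 0.0550 + 0.1787 + 0.2680 + 0.2457 = 0.747. Expected N = 13 + 0.2527 × 13 = 16.28. Alpha 0.0498, power 85.1%.

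Everything agrees with the plan. The printed 0.049 for Group 3a is 0.0498 truncated.

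**Step 2: add the overrun.** If m patients are enrolled before the decision, a stopped group ends with n₁ + m patients. A continuing group still ends with n, as long as m does not exceed n − n₁. So

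expected N = PET × (n₁ + m) + (1 − PET) × n = printed expected N + PET × m.

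Each extra patient adds 0.648 in Group 1 and 0.747 in Group 3a. With a 12-week evaluation, m of 3, 6 and 9 corresponds to roughly 1, 2 and 3 patients per month in that group.

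| m (assumed) | Group 1 | Group 3a |
|---|---|---|
| 0 (as printed) | 25.91 | 16.28 |
| 3 | 27.9 | 18.5 |
| 6 | 29.8 | 20.8 |
| 9 | 31.7 | 23.0 |
| 13 | 34.3 | 26.0 |

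At m = 13, Group 3a is fully enrolled before the decision and early stopping spares nobody.

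**Step 3: error rates under overrun alone.** If the decision rests on the planned 15 or 13 patients and the printed cuts are kept, the later patients do not alter which outcomes lead to an efficacy call. Alpha stays at 0.0498 in both groups, and power stays at 70.5% and 85.1%.

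**Step 4: a changed null (hypothetical illustration only).** Suppose the null were reset to 15%, the Stage 1 cut kept, and the final cut re-derived as the smallest with alpha ≤ 0.05. The cuts become ≥11/46 (alpha 4.4% at 15%) and ≥7/26 (alpha 4.9% at 15%). At a true rate of 20% the chance of an efficacy call is then 19.3% in Group 1 and 15.8% in Group 3a, against 5.0% under the printed cuts. A reset to 25% works the other way: ≥17/46 and ≥11/26 give 0.5% and 0.8% at a true 20%.

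**The case against.** The strongest reply is that nothing is miscalculated. Every figure reproduces, and Protocol 8.3 presents them as properties of the optimal Simon criterion. That is right: the fault is an operating assumption that the plan's own enrolment sentence contradicts.

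A reader might infer that continued enrolment makes the stated alpha and power wrong. The documents do not support this; step 3 shows both are unchanged when Stage 1 is judged on its planned patients with the printed cuts. A reader might also infer that the sponsor intends to revise the 20% null after seeing responses. The text does not say so. It names a rate update as one example of why extra patients could be useful, and the SAP keeps the rates and cuts. The 19.3% and 15.8% figures therefore describe something the wording permits, not something it plans. If 15% were legitimately the right null, they would be power at 20%.

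Nor does overrun necessarily remove the benefit of the design. Against single-stage enrolment of 46 and 26, the printed designs save 20.1 and 9.7 patients on average under the null. At m = 6 they still save 16.2 and 5.2. Complete loss in Group 3a needs 13 patients in about 12 weeks, more than 4 per month.

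The consequence is also limited because objective response is a secondary endpoint, the sample sizes are described as guided by the Simon designs, and the design table speaks of considering futility or efficacy. This lowers the priority. It does not remove the conflict, since Protocol 8.3 also states firm stopping rules, and the missing cap and the conflict with the Synopsis stand.

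**Conclusion.** The point holds for expected sample size. The printed 25.91 and 16.28 are not the values for a trial that keeps enrolling during the Stage 1 evaluation. They understate expected exposure under the null by 0.648 and 0.747 patients for each patient enrolled meanwhile. Over the assumed range of 3 to 9 that is about 2 to 6 patients in Group 1 and 2 to 7 in Group 3a. The size depends on accrual and on an evaluation of about 12 weeks, neither of which the documents state.

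For alpha and power the supported conclusion is narrower: the printed values are correct for the printed rules, but not guaranteed while a rate update is left open with no rule on timing or on the cuts. This should be corrected, but it does not threaten the primary safety objective.

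**What to change.** 1. In Protocol 8.3 and Phase 2a SAP 4, state a maximum number of patients who may be enrolled in each group during the Stage 1 evaluation, and restate expected N under that cap using the formula above. Bring the Synopsis text for Group 3a, Protocol 3.5.1, the Stage 1 total of about 28, and SAP 2.3 and 4 into line with it.
2. State that Stage 1 is judged on the first 15 (Group 1) or 13 (Group 3a) evaluable patients in order of first dose, and that later patients do not enter that count. Using evaluable patients agrees with Protocol 3.5.1, which sets the Group 3a review at 13 evaluable patients, and with the stated aim of covering non-evaluable participants.
3. Delete the historical-rate update as an example. State that the null and target rates and all cuts are fixed, and that any change is made only by amendment before Stage 1 responses are reviewed.

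The cost is protocol and SAP wording, and a printed expected sample size that looks less favourable. No patients are added. Pausing enrolment at 15 or 13 would also make the printed figures true, but could halt accrual for about 12 weeks and is not needed.
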